## **13.3 Analysis of Safety**

### **13.3.1 Adverse events (non-serious or serious)**

AEs will be coded using the MedDRA. The version of the utilized dictionary will be presented either in the title or footnote of the provided tables and by-patient listings. Events will be identified as treatment-emergent (TEAE) and non-treatment-emergent (Non-TEAE) on the basis of the date of onset relative to the date of the first IMP dose. Events with an onset date before the date of the first IMP dose will be defined as Non-TEAE. Events with an onset date on or after the first IMP dose or pre-existing and worsening after IMP intake will be defined as TEAE.

---

For all TEAEs occurring during the first 4 weeks of treatment (on or before Visit 3), and separately for all TEAEs (i.e. events with onset at any time during randomized treatment, as secondary assessment, please refer to section 8.4), a summary containing the following counts and percentages of subjects will be presented by treatment group and overall:

- Overview table, including the number (percent) of patients with
  - Any TEAEs
  - Mild TEAEs
  - Moderate TEAE
  - Severe TEAEs,
  - Serious TEAEs
  - Treatment-related TEAEs,
  - Serious Treatment-related TEAEs,
  - COVID-19 related TEAEs;
  - TEAEs leading to discontinuation of study,
  - TEAEs leading to discontinuation of treatment,
  - TEAEs having an outcome of death.

AEs leading to discontinuation of study are identified as AEs whose CRF field in AE form “Study discontinued due to this (S)AE” is flagged as “Yes”.

AEs leading to discontinuation of treatment are identified as AEs whose CRF field in AE form “Action taken” is flagged as “Treatment stopped”.

Patients who have multiple events will be counted only once but all events will be considered as occurred.

Summaries (number of events as well as number and percentage of patients with any events of a particular type) of TEAEs will be provided by primary system organ class (SOC) and preferred term (PT) and will be ordered in terms of decreasing frequency for SOC, and PT within SOC, in the total column. Patients who have multiple events coding to the same PT or within the same SOC will be counted only once in the patient counts for the corresponding summaries, but all events will be considered and listed. Patients who experience the same event multiple times will be included in the most severe category where applicable.

Summaries of TEAEs by primary system organ class (SOC) and preferred term (PT) will be presented for all TEAEs occurring during the first 4 weeks of treatment (on or before Visit 3), and separately for all TEAEs (as secondary assessment-please refer to section 8.4).

Number of events and number (%) of patients experiencing TEAEs by maximum severity (mild, moderate, and severe), relationship to IMP, and action taken with regard to IMP will be summarized.

---

Number (%) of events and of patients with TEAEs leading to discontinuation of clinical trial participation as well as treatment discontinuation will also be summarized.

Tables will be provided also for TEAEs related to COVID-19 (as described in section 16.3), for related TEAEs, for serious TEAEs, for serious TEAEs by seriousness criteria, for serious TEAE by relationship and for serious -related TEAEs.

Treatment group comparisons of the proportion of patients with TEAEs will be based on Wilson score confidence intervals (Wilson, 1927). Pairwise comparisons between all treatment groups will be provided at the SOC level for TEAEs occurring on or before Visit 3, and for all TEAEs (as secondary assessment-please refer to section 8.4).

Incidence densities of events per patient day starting with the first IMP administration will be determined for all TEAEs. In accordance with the visit schedule, incidence densities will be provided for the periods between every two adjacent visits starting with the first IMP administration. Additionally, the overall of all incidence densities and the sum of the incidence densities during the first 4 weeks of treatment (on or before Visit 3) will be presented.

In addition to the pairwise treatment group comparisons, all analyses specified above in this section will also be performed for the comparison between all patients treated with L-CsA (2 x 5 mg/day or 2 x 10 mg/day) and those treated with placebo in order to increase the chance of identifying TEAEs potentially related to L-CsA.

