12.1.1 Definitions

Adverse Event (AE)

An AE is any untoward medical occurrence in a patient after administration of a pharmaceutical product and which does not necessarily have a causal relationship with this treatment. An AE can therefore be any unfavorable and unintended sign (including an abnormal laboratory finding), symptom, or disease temporally associated with the use of a medicinal (investigational) product, whether or not related to the medicinal (investigational) product (ICH Guidelines for Good Clinical Practice E6(R2), 9 November 2016).

This includes worsening of a pre-existing condition or increase in frequency of a pre-existing condition. An AE is considered serious if it meets any of the serious criteria listed below. To ensure no confusion or misunderstanding of the difference between the terms “serious” and “severe”, which are not synonymous, the following clarification is provided:

The term “severe” is often used to describe the intensity (severity) of a specific event (as in mild, moderate, or severe myocardial infarction); the event itself, however, may be of relatively minor medical significance (such as severe headache). This is not the same as “serious”, which is based on patient/event outcome or action criteria usually associated with events that pose a threat to a patient’s life or functioning. Seriousness (not severity) serves a guide for defining regulatory reporting obligations.

The official definition also extends to AEs occurring during the off-treatment follow-up period.

Each patient will be closely observed and questioned for AEs throughout the clinical trial period with non-leading questions (e.g., how do you feel?). The patients will be instructed to report to the clinical trial staff immediately any symptoms and/or signs which occur between the scheduled observation times.

All AEs reported by the patient or observed by the Investigator or hospital personnel will be documented in the respective eCRF. The following information regarding each AE will be obtained: date and time of onset and resolution (duration), serious or non-serious (as defined below), severity, treatment required, outcome, relationship to certain medication, and if the AE caused withdrawal from the clinical trial.

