12.1.8 Physical Examinations

A physical examination will be carried out at the Screening Visit and at every subsequent on-site visit. The following body systems will be examined: body weight and height (at Screening visit only), cardiovascular, respiratory, nervous, gastrointestinal, hepatic, renal, dermatological, musculoskeletal, extremities, eyes, ears, nose, throat, and lymphatic.

Abnormal findings will be summarized for each patient and will be documented as AE.

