13.2.2 Visit 1 / Baseline Visit / Randomization

Baseline Prior to Start of Treatment

- Verify Informed Consent was obtained
- Verify Demographics/Medical History
- Repeat Urine/Serum Pregnancy Test (Urine samples can be collected at the Randomization Visit in order to obtain results quickly while the patient is in the clinic and not delay randomization)
- Physical examination
- Vital signs
- Clinical laboratory tests
- PK blood sample pre-dose
- Spirometry
- Randomization
- Concomitant medications/therapies
- AEs
- CGI (Item 1 only)
- SF-36 questionnaire

Start of Treatment

Following activities will be performed:

- Train patient on L-CsA **CCI** use, drug storage, and inhalation technique
- IMP Administration. Supervise first inhalation for proper use of the nebulizer and for tolerability issues.
- Verify patient is familiar with drug administration and use of nebulizer device
- Emphasize importance of adherence to IMP
- Emphasize importance of adherence to usual medications as taken prior to participating in the trial
- Spirometry: (1 hour \pm 20 minutes after completion of dosing with IMP)
- PK blood samples directly after end of inhalation, 15, 30, and 45 minutes (+/- 5 min), and 1, 1.5, 2, and 4 hours (+/- 15 min.) after end of inhalation
- Local IMP tolerability

Prior to release from clinic, study drug and the nebulizer system for home use will be dispensed to each patient. Patient will receive full IMP supply for the 12 weeks treatment period.

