### **9.1.1 Imputation of Missing data**

There will be no imputation of data for efficacy analysis. All data will be analyzed as they appear in the database. Missing data will be displayed in subject data listings and will be declared in tables as appropriate.

The following imputation rules will apply only for AE data:

- Imputed data should be flagged and properly footnoted as “imputed”.
- AEs with unknown onset date/time will be counted as treatment emergent AEs (TEAEs).
- AEs/TEAEs with unknown end date/time will be counted as an ongoing AEs/TEAEs, unless ongoing was ticked on the CRF.
- TEAEs will be considered potentially IMP related if the investigator’s rating of the causal relationship is anything other than ‘not related’ or missing.
- If for the calculation of a time period the full date format ddmmmyyyy is needed, missing entries will be imputed as follows:
  - Missing day in start date of a time period is imputed by the first day of the month;
  - Missing day in stop date of a time period is imputed by the last day of the month;
  - Missing month in start date of a time period is imputed by January of the year;
  - Missing month in stop date of a time period is imputed by December of the year;
  - Missing year is not imputed.

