## 10.3 Definitions Related to Safety Data

### 10.3.1 Treatment-emergent Adverse Events

Treatment-emergent adverse events (TEAEs) are defined as AEs with onset on or after the IMP intake or pre-existing and worsening after IMP intake.

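### TEAEs are classified by onset date alone, so an adverse event that starts on Day 1 before the first inhalation counts as treatment-emergent

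*SAP*

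**What the plan says.** SAP 13.3.1 sorts adverse events into TEAE and Non-TEAE "on the basis of the date of onset relative to the date of the first IMP dose". It then fixes the boundary: "Events with an onset date before the date of the first IMP dose will be defined as Non-TEAE". An event dated on the day of the first dose is therefore never Non-TEAE under that sentence. Protocol 14.2.3.2 compares the same two dates.

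SAP 10.3.1 gives a second definition: "Treatment-emergent adverse events (TEAEs) are defined as AEs with onset on or after the IMP intake", or already present and worse after intake. Its reference point is the intake, not the calendar day.

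The first dose is given at Visit 1. Protocol 13.2.2 lists a block of procedures under "Baseline Prior to Start of Treatment": physical examination, vital signs, laboratory tests, the pre-dose PK sample, spirometry and recording of adverse events. On physical examination, Protocol 12.1.8 says: "Abnormal findings will be summarized for each patient and will be documented as AE". It makes no exception for the pre-dose examination.

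For each adverse event, Protocol 12.1.1 collects the time of onset as well as the date. The listing in SAP 16.2 includes the date and time of IMP administration.

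**The concern.** An event that begins before the first inhalation cannot have been caused by the IMP. The date rule nevertheless counts it as treatment-emergent when it falls on Day 1. Two kinds of event are exposed: reactions to the pre-dose procedures themselves, and signs that are new since Screening and are given the Visit 1 date as their onset.

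TEAEs up to Visit 3 are part of the primary assessment. They enter the overview table, the tables by system organ class and preferred term, the pairwise Wilson comparisons by system organ class, the incidence densities and the pooled L-CsA versus placebo comparison. Events unrelated to allocation raise the proportion in every arm and, on average, pull the arms together.

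The two SAP definitions add a practical problem. A programmer working from 10.3.1 and one working from 13.3.1 could produce different TEAE counts from the same data.

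**Working it through.** **Passages side by side**

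| Adverse event | SAP 13.3.1 (date) | SAP 10.3.1, read by time of intake |
|---|---|---|
| Onset before Day 1, no worsening | Non-TEAE | Non-TEAE |
| Onset on Day 1, before the first inhalation, no worsening | TEAE | not a TEAE |
| Onset on Day 1, after the first inhalation | TEAE | TEAE |
| Onset date and time unknown (SAP 9.1.1) | TEAE | TEAE |

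Only the second row differs. For events in that row, SAP 13.3.1 also disagrees with its own incidence densities: the event enters the numerator, while the patient-days in the denominator start at the first administration.

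**What is not touched.** SAP 13.1 accepts a local tolerability event only if it appears within 1 hour after the end of an inhalation, so a pre-dose event cannot qualify.

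**Size.** The plan states no event rate, power or effect size to reproduce. Its only relevant figures are 24 patients, 8 per arm, and two-sided 95% intervals. Everything else here is assumed.

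- q: share of patients with a pre-dose Day 1 adverse event, equal across arms and independent of later events (assumed).
- p: true proportion with a TEAE; 62.5% in one arm and 25% in the other for illustration (assumed).

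The proportion counted under the date rule is p' = 1 - (1 - p)(1 - q). The difference between two arms is then (1 - q)(p1 - p0). The last two columns give the probability that the 95% interval for the difference lies wholly above zero, by exact binomial enumeration. The SAP does not say how the Wilson limits are combined for a difference; the Newcombe form is assumed.

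| q | Counted proportions | Difference (points) | At least one such patient in 24: 1 - (1 - q)^24 | 8 v 8 | Pooled, 16 v 8 |
|---|---|---|---|---|---|
| 0 | 62.5% v 25.0% | 37.5 | 0 | 40.5% | 45.4% |
| 5% | 64.4% v 28.8% | 35.6 | 71% | 37.5% | 41.9% |
| 10% | 66.2% v 32.5% | 33.8 | 92% | 34.6% | 38.7% |
| 20% | 70.0% v 40.0% | 30.0 | 99.5% | 28.8% | 33.0% |

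**One patient.** In an arm of 8, a patient counted only because of a pre-dose event adds 1/8 = 12.5 points. A patient who has another TEAE in the same table adds nothing, hence up to 12.5.

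- 5/8 v 2/8: 37.5 points (95% interval -9.2 to 67.3, width 76.5).
- One such patient added to the lower arm, 5/8 v 3/8: 25.0 points (-20.1 to 58.7).
- One such patient added to the higher arm instead, 6/8 v 2/8: 50.0 points.

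Shrinkage is therefore the expected direction, but a single contrast in this trial can move either way.

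**The case against.** The strongest reply is that few events will be affected. The rule depends on when an event began, not on when it was written down. A reader might infer that any abnormality first recorded at the Visit 1 examination becomes a TEAE, so that long-standing chronic GvHD signs push every arm towards 100%. The documents do not support this. An onset dated before Day 1 is Non-TEAE unless the condition worsens. Protocol 12.1.8 and 13.2.1 put the same body-system examination at Screening, up to 4 weeks earlier, and 13.2.1 records chronic GvHD in other organs as medical history. What remains is mainly events that start, or are dated as starting, on the morning of Visit 1. A high q is therefore hard to defend.

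A reader might also infer that the whole primary assessment is diluted. It is not: local tolerability is protected, and the pairwise TEAE comparisons are made by system organ class, where q is no larger than for any TEAE and usually smaller. Events rated unrelated stay out of the treatment-related tables. At q of 5% to 10% the loss is about 2 to 4 points of 37.5, beside an interval 76.5 points wide, in a plan that is purely descriptive.

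It can also be said that the date rule errs towards inclusion, in line with SAP 9.1.1, and that a time rule could drop a true post-dose event whose time was misrecorded.

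All of this limits the size, and the last point is a real, if small, cost. None of it removes the inconsistency. Including pre-dose events is cautious for a listing but not for a comparison between arms. The closing sentence of the rule in 13.3.1 does refer to the first dose, but the sentence before it sets the Non-TEAE boundary by date.

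**Conclusion.** The point holds in a limited form. As written, SAP 13.3.1 and Protocol 14.2.3.2 count an adverse event with onset on Day 1 before the first inhalation as treatment-emergent. This conflicts with SAP 10.3.1 read by intake and with the time origin of the incidence densities, although the data needed to separate such events are collected. It reaches the TEAE tables and the comparisons by system organ class, up to Visit 3 and over the whole treatment period. It does not reach the local tolerability analysis.

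The size is unknown because the documents give no q. Under equal and independent q, the expected difference falls by 5% to 10% at q of 5% to 10%; one misclassified patient moves an arm by up to 12.5 points, and chance imbalance can turn that in either direction. No error rate or sample size figure changes, since the plan sets none.

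**What to change.** Align SAP 10.3.1 and 13.3.1 on one rule:

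- An adverse event on the date of the first dose, with a recorded onset time before the start of the first inhalation, is Non-TEAE unless it worsens after intake.
- A Day 1 event with a missing onset time stays a TEAE, in keeping with SAP 9.1.1.
- All Day 1 events classed as Non-TEAE appear in a separate listing, so that a misrecorded time near the first inhalation can be seen and checked.

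The cost is a short SAP revision and one extra listing, with no new data collection. SAP 6 and Protocol 14 give the SAP precedence, so the core change needs no protocol amendment. It should be entered in the SAP 6 table of differences, because Protocol 14.2.3.2 keeps the date rule. A sentence in Protocol 12.1.8 on findings already present before the first dose would help but is not required, and it would be a protocol change.

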## **9.2 Sample Size Considerations**

This is a Phase IIa study in a rare indication, with very limited availability of eligible patients and a purely descriptive statistical concept. Accordingly, the sample size for the study was established based on considerations of feasibility rather than on power calculations.

A total of 24 patients (3 arms with 8 patients in each) are planned to be randomized.

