## 13 PRIMARY ASSESSMENTS

The primary assessments will be measures of safety and local tolerability listed in Section 8.3 and covering the first 4 weeks of treatment, defined as data collected until Visit 3. AEs will be included into this analysis if their date of onset lies on or before Visit 3 or, in case of an incomplete or missing date of onset, if they could have started on or before Visit 3 in accordance with all available information, using the procedure for incomplete data information already described in Section 12 above.

Outcomes assessed during study visits will be included into the primary analysis up until Visit 3 scheduled to be performed at Week 4 after baseline, or until the EoT visit if it was performed on or before Visit 3.

All analyses described in this chapter will be performed on the SAF.

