### 13.1 Analysis of Local Tolerability

In accordance with the study protocol, local tolerability events of interest (i.e., cough, wheezing, bronchospasm, throat irritation, and change in FEV1) will be documented in the eCRF as AEs. During data analysis local tolerability events of interest thus have to be identified from the CRF form of AEs as follows:

- MedDRA (version 23.1) Preferred Terms (PTs):
  - Cough (MedDRA code 10011224)
  - Wheezing (MedDRA code 10047924)
  - Bronchospasm (MedDRA codes 10006482, 10072338)
  - Throat irritation (MedDRA code 10043521)
  - Change in FEV1 (MedDRA codes 10016987, 10016989, 10016985)
- The version of the utilized dictionary will be presented either in the title or footnote of the provided tables and listings.
- The event must have newly appeared within 1 hour after the end of an IMP inhalation.
- They must have occurred within on or before Visit 3.
- Events meeting the criteria above will be selected independently of the causality assessment of the investigator.

For each local tolerability event, pairwise treatment group comparisons of the proportion of patients with at least one local tolerability event will be performed based on Wilson score 95% confidence intervals (Wilson, 1927).

---

Moreover, incidence densities of events per patient treatment day starting with the first IMP administration will be determined separately for each local tolerability event. In accordance with the visit schedule, incidence densities will be provided for the periods between every two adjacent visits starting with the first IMP administration for the entire randomized treatment period up until Visit 3, and for entire randomized treatment period (as secondary assessment, please refer to section 8.4). Events will be assigned to their period of onset.

In addition to the pairwise treatment group comparisons, all analyses specified above in this section will also be performed for the comparison between all patients treated with L-CsA (2 x 5 mg/day or 2 x 10 mg/day) and those treated with placebo.

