## **14 SECONDARY ASSESSMENTS**

### **14.1 Local and Overall Tolerability, and Safety**

In the context of secondary assessments i.e. IMP tolerability and safety during the first 12 weeks of treatment, all analyses described in Section 13 will be performed for the entire randomized treatment period.

For all tabulations broken down by visit, no separate tabulations for primary and secondary assessments are required as the results for the period up until Visit 3 are a subset of those for the entire period of observation and can thus be taken from the same table.

All analyses will be carried out in the SAF set.

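### Read literally, SAP 13.3.1 reports the first-4-week TEAE incidence density as a sum of two period rates, about twice the actual density

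*SAP*

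**What the plan says.** SAP 13 defines the primary safety and tolerability window as "covering the first 4 weeks of treatment, defined as data collected until Visit 3".

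For all TEAEs, SAP 13.3.1 sets the unit: "Incidence densities of events per patient day starting with the first IMP administration will be determined for all TEAEs". It then sets the periods: "incidence densities will be provided for the periods between every two adjacent visits starting with the first IMP administration". The next sentence adds two summary figures. One is an overall figure, with no formula. The other is the 4-week figure: "the sum of the incidence densities during the first 4 weeks of treatment (on or before Visit 3) will be presented".

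For local tolerability events, SAP 13.1 also asks for densities between adjacent visits, but its summary figures are densities "for the entire randomized treatment period up until Visit 3, and for entire randomized treatment period". No sum is mentioned.

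SAP 14.1 carries the work over to 12 weeks: "all analyses described in Section 13 will be performed for the entire randomized treatment period". Protocol 14.2.3.2 asks for densities per between-visit period and for the whole treatment period, again with no sum. The table of differences from the protocol in SAP 6 lists only the renaming of protocol deviation categories. SAP 6 also says that the SAP governs where the two documents conflict.

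**The concern.** An incidence density is a rate. Adding the rates of two consecutive intervals does not give the rate over the combined interval, any more than adding the average speeds of two halves of a journey gives the speed of the whole. The combined rate is a patient-time-weighted mean of the two and cannot exceed the larger.

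A programmer who follows 13.3.1 as written would add the Visit 1 to 2 and Visit 2 to 3 rows and label the result as events per patient day over the first 4 weeks. That figure would be on a different scale from the interval rows beside it and from the 4-week densities of SAP 13.1, although the nominal unit is almost the same. It is the only 4-week density planned for all TEAEs, and it falls in the primary window. The same section repeats its analyses for the two L-CsA arms combined against placebo, so the figure would enter that comparison too.

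**Working it through.** The documents give no value for this figure, so there is nothing to reproduce. The check compares the literal rule with the definition of a density.

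**Inputs from the documents**
- Unit and intervals: SAP 13.3.1.
- Visit 2 at Week 2 ± 3 days and Visit 3 at Week 4 ± 3 days (SAP Table 1), so about day 11 to 17 and day 25 to 31. The nominal intervals are 14 and 14 days.
- 8 patients per arm (SAP 9.2).

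**Assumed:** event counts and the change in rate between intervals. The documents give no TEAE rate.

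**Formulas.** With E events and T patient-days in intervals 1 and 2:
- Literal sum: S = E1/T1 + E2/T2
- 4-week density: D = (E1 + E2)/(T1 + T2)
- With interval rates r1 and r2: S/D = (r1 + r2)(T1 + T2)/(r1·T1 + r2·T2)

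If T1 = T2, S/D = 2 whatever the event counts. If r1 = r2, S/D = 2 whatever the interval lengths or drop-out.

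**Nominal schedule.** 8 patients × 14 days = 112 patient-days per interval; assume 8 then 4 events.
- Interval densities: 8/112 = 0.071 and 4/112 = 0.036
- S = 12/112 = 0.107, above both
- D = 12/224 = 0.054, between them
- S/D = 2.00

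As a sense check, 12 events in 8 patients is 1.5 per patient. D × 28 days gives 1.5; S × 28 days gives 3.0.

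**Visit-window limits, twofold rate change assumed** (days per patient)

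| T1, T2 | rates 2:1 | rates 1:2 |
|---|---|---|
| 17, 8 | 3×25/42 = 1.79 | 3×25/33 = 2.27 |
| 11, 20 | 3×31/42 = 2.21 | 3×31/51 = 1.82 |

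The range is about 1.8 to 2.3.

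**Loss of patients at Visit 2** (14-day intervals, same twofold assumption). With 4 of 8 lost, T1 = 112 and T2 = 56: 3×168/280 = 1.80 and 3×168/224 = 2.25. With 1 of 8 lost, T2 = 98: 1.96 and 2.05.

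**Between-arm ratio.** It is preserved when S/D is the same in both arms. Equal patient-time in the two intervals within each arm, or a constant rate in each arm, guarantees this. Equal patient-time across arms does not. Take T1 = 8×17 = 136 and T2 = 8×8 = 64 in both arms, which is inside the windows:
- Arm A, 8 then 4 events: D = 12/200 = 0.060; S = 8/136 + 4/64 = 0.1213
- Arm B, 4 then 8 events: D = 12/200 = 0.060; S = 4/136 + 8/64 = 0.1544

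The ratio of densities is 1.00; the ratio of sums is 0.1213/0.1544 = 0.79. This is a constructed extreme: arm B's rate rises more than fourfold, from 0.029 to 0.125.

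**The case against.** The best defence is that the word sum is loose wording for pooled totals. The other half of the same sentence is loose too, since it asks for an overall figure without defining it. SAP 13.1 uses a whole-period density for local tolerability, the protocol sets one method for both kinds of event, and SAP 6 declares no change of method. SAP 5 places the programming specifications in a separate document, so the intended calculation cannot be checked here. This stands as far as intent goes: the error is conditional on the literal reading. It does not remove the point. The SAP prevails over the protocol, and 13.3.1 states a sum immediately after defining the interval densities.

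The second defence is weight. The study is descriptive, with no type I error control and no primary hypothesis or model, and this is one row. The anomaly might be noticed, because the 4-week figure would exceed both interval rows whenever each has events. Nor does any document plan to scale the figure to 28 days; that step above is only a sense check. All of this is fair, and it limits the harm to the level of one figure.

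A reader might also infer that the 12-week overall density is a sum. Over four intervals it would then be four times the true density at a constant rate. The text does not say sum for that figure, and SAP 14.1 can be read as a proper whole-period analysis, so the documents do not support that charge. They support only the remark that the overall figure is undefined.

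**Conclusion.** The point holds for the wording of SAP 13.3.1. Followed literally, it gives a 4-week all-TEAE density exactly 2.00 times the actual one at the nominal schedule or at a constant rate. The factor is about 1.8 to 2.3 at the visit-window limits under an assumed twofold rate change. The factor of two follows from the schedule alone; the range around it rests on the assumed rates.

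Between-arm differences would be inflated by the same factor when it is common to the arms. Between-arm ratios are then unchanged, but they can be distorted when the two intervals differ in patient-time and the rates change differently by arm. Event and patient counts, percentages, Wilson intervals and per-interval densities are unaffected.

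It would go too far to infer that the sponsor will certainly report doubled rates, or that the 4-week safety comparison as a whole is unsound. The documents show an instruction that yields the wrong figure if followed, in one descriptive row of the primary window.

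**What to change.** Replace the sentence in SAP 13.3.1 with wording such as:

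*Additionally, the incidence density for the first 4 weeks will be presented as the total number of TEAEs (as defined in Section 10.3.1) assigned to the period from first IMP dose up to Visit 3 under the date rules of Sections 9.1.1 and 13, divided by the total patient-days in that period. The overall density for the randomized treatment period will be calculated in the same way, not as a sum of period densities.*

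Two details matter. The numerator should refer to the TEAE definition and the date rules rather than to onset alone. Otherwise, pre-existing events that worsen after dosing and events with incomplete dates could be lost. The per-interval and pooled rows should use the same patient-day denominator, and the SAP should state which one. SAP 13.1 counts treatment days and 13.3.1 counts patient days, and under Protocol 9.3.1 patients who stop IMP are asked to continue their visits.

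The cost is one SAP sentence, documented as a modification as SAP 5 requires, and a trivial programming change. Data collection is not affected.
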